2.10 Type 1 Error Control for Multiple Tests

Not applicable. This is an exploratory, hypothesis generating study. All efficacy analyses are considered exploratory.

2.11 Handling of Missing Data

The primary efficacy analysis will be based on observed cases (i.e. no missing data imputation). Sensitivity analyses will be performed using various missing data imputation approaches as described in Section 5.1.

All analyses unless specified will be conducted on an as observed case basis, that is, no further imputation of missing data will be carried out unless expressly stated otherwise.

Imputation for Missing Concomitant Medication and AE Start and Stop Days:

Missing and/or incomplete dates for concomitant medications and AEs will be imputed for calculating Start/Onset Day and Stop Day only. The Start/Onset Day

and Stop Day may be used for calculating prior or concomitant medications or calculating treatment emergent AEs. Missing and/or incomplete dates will be imputed in a manner that assumes the worst case scenario (i.e. Start/Onset as close as possible to the First Study Treatment Administration and stopped such that it assumed to have lasted for the longest possible duration, taking into account that the Start/Onset date should not be after the Stop date).

Imputation for missing Stop Date:

- For a completely missing stop year (regardless of day or month) the medication/AE will be assumed to be ongoing.
- For a missing stop month (and a medication/AE that is not 'Ongoing') the medication/AE will be assumed to have ended the last available month of that year.
- For a missing stop day (and a medication/AE that is not 'Ongoing') the medication/AE will be assumed to have ended on the last day of the month if the month is available.

Imputation for missing Start/Onset Date:

- For a completely missing Start/Onset date (day, month and year), the Start Day of medication/AE will be considered pre-treatment (i.e. prior) if the stop date or partial stop date concludes the medication/AE was stopped before the first administration of the study product. In all other instances (i.e. inconclusive stop date or Ongoing medication/AE) the Start Day of medication/AE will be assumed to have started at the date of the first administration of the study product (i.e. assumed to be concomitant or treatment emergent as is applicable).
- For a missing start/onset month the medication/AE will be assumed to have started in January of that year, or at the date of first administration of the study product if the start/onset year was the same as the year of first administration of the study product.
- For a missing start/onset day the medication/AE will be assumed to have started on the first day of the month, or at the date of first administration of the study product and the year was the same as the Randomization month and year.

3 SUBJECT INFORMATION

In general, all subject information will be summarized for the FAS Population, unless stated otherwise.

3.1 Disposition Information

Summaries will be provided for number and percentage of completed or discontinued study with the reasons of discontinuation as collected on eCRF.

3.2 Study Visits

The number and percentage of subjects completing each scheduled visit will be tabulated.

3.3 Demographics Characteristics

Descriptive statistics or frequency tabulation will be provided for age, gender, race, and ethnicity.

3.4 Medical and Ocular History and Surgical Procedures

A summary table will be prepared for the medical history/surgical procedure data, and one for ocular history/surgical procedure data. Conditions will be categorized according to MedDRA-coded terms. This table will indicate the number and percentage of subjects who presented with previous history overall and by system organ class (SOC) and preferred term (PT). SOC will be sorted alphabetically and PT within each SOC will be sorted by overall descending order of frequency.

The initial diagnosis of neurotrophic keratitis/keratopathy will be included in a listing.

3.5 Pregnancy Status

The data for urine pregnancy testing will be presented in a listing, for female subjects with childbearing potential only.

3.6 **Protocol Deviations**

All reported protocol deviations and determined exclusions from any analysis population(s) will be documented and included in the CSR. All reported protocol deviations and inclusion or exclusion exceptions will be included in a listing.

4 TREATMENTS AND MEDICATIONS

In general, all treatment parameters will be summarized for the Full Analysis Set, unless stated otherwise. All reported medications will be coded using World Health Organization-Drug Dictionary (WHO-DD). For summary of medications, the coded generic medication name (Preferred Term) will be sorted by overall descending order of frequency.

4.1 **Prior Medications**

Prior medications are medications that discontinued prior to receiving the first administration of the study product at Day 1 based on imputed stop day. Summary tables will be prepared for the reported use of all prior medications by generic name and location (ocular vs non-ocular).

4.2 Concomitant Medications

Concomitant medications include all medications that a subject used during the study on or after the first administration of the study product at Day 1. Summary tables will be prepared for the reported use of all concomitant medications by

generic name and location (ocular vs non-ocular), and further classified as On Treatment Period (medications started between the day of first administration of the study product and the day of last administration of the study product), and On Follow-up Period (medications started after the day of last administration of the study product).

4.3 Use of Artificial Tears

Use of artificial tears during the washout period is calculated as days on the use of artificial tears, defined as one plus the difference in days between date of last instillation of artificial tears and the date of first instillation of artificial tears during the washout period. Use of artificial tears will be summarized by descriptive statistics.

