1. STUDY SYNOPSIS

CLINICAL STUDY SYNOPSI	S:				
Study Number	NGF0120				
Title of Study	An 8-week, multicenter, open label, prospective study with 24 weeks of follow-up to evaluate safety and efficacy of OXERVATE™ 0.002% (20 mcg/mL) cenegermin-bkbj ophthalmic solution in patients with Stage 1 Neurotrophic Keratitis (NK)				
Short Title	DEFENDO				
EudraCT N°/IND	115892				
Study Centers (Country)	Approximately 5 US study centers				
Development Phase	IV				
Objectives	Primary Objective The primary objective of this study is to evaluate the safety and efficacy of OXERVATE™ 0.002% (20 mcg/mL) cenegermin-bkbj ophthalmic solution administered 6 times daily for 8 weeks on the ocular surface, visual function and quality of life in patients with Stage 1 NK. Secondary Objective The secondary objective is to evaluate patients who heal at week eight and remain healed (as defined in section 3.3) throughout the follow-up period. In addition, the study aims to evaluate the percentage of subjects that achieve an improvement in corneal sensitivity as measured by the Cochet-Bonnet aesthesiometer at 4 and 8 weeks, and by the last visit week 32. Exploratory Objectives The exploratory objectives are to evaluate the change from baseline to weeks 4 & 8 in Schirmer I and the Tear Film Break-Up Time (TFBUT). Additional Objectives (site specific) The additional objectives are to evaluate the change from baseline at week 8 and week 24 in confocal microscopy and anterior segment Optical Coherence Tomography (OCT).				

This clinical study will be a multi-center, open label, prospective study of 8 weeks of treatment with 24 weeks of follow-up to evaluate the safety and efficacy of OXERVATE 0.002% (20 mcg/mL) cenegermin-bkbj ophthalmic solution administered as one drop in the affected eye(s), 6 times per day at 2-hour intervals, for eight weeks in patients with Stage 1 Neurotrophic Keratitis (NK). The study is divided into four phases as follows:

- 1. Screening Visit (Day -14): Procedures for inclusion will be performed at both Visit 1 (Screening) and Visit 2 (Baseline). Commercially available artificial tears (AT) provided by the sponsor will be permitted during the Screening period as needed up to four times a day.

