- 2. Washout period (from day minus 14 to day 0): 14 days with no further treatment except commercially available preservative-free artificial tears provided by the sponsor (Note: Xiidra[™] and Restasis[™] use is disallowed for 14 days prior to Visit 2.) Artificial tears (AT) provided by the sponsor will be permitted up to four times a day and will be tracked via daily diary during washout period.

3. **Treatment:**

- a. Treatment (weeks 1-8): eligible patients will start OXERVATETM 0.002% (20 mcg/mL) cenegermin-bkbj ophthalmic solution administered as one drop in the affected eye(s), 6 times per day at 2-hour intervals, for eight weeks. During the treatment period, only study product will be permitted for topical ocular treatment.

 Commercially available preservative free artificial tears (AT) provided by Sponsor are not allowed during the treatment period except as rescue therapy.
- 4. Follow up (weeks 9-32): For the 24 weeks post treatment:
 - a. For patients completely healed, no treatment is allowed except for commercially available AT provided by the Sponsor, administration frequency is at the physician's discretion during follow-up based on patients need for

Study Design and Methodology

- lubrication. The use of artificial tears will be tracked via a daily dosing diary.
- b. For patients not completely healed and who don't meet criteria for premature discontinuation, will also be followed up but any topical treatment is allowed at the discretion of the physician. All treatments will be tracked as concomitant medications. No surgical procedures are permitted during the follow-up (i.e. sutured Amniotic Membrane Transfer (AMT), sutured tarsorrhaphy). Permitted items include topical medications and suture less AMT.

The study will be a total of 34 weeks in duration: a screening period of 2 weeks, followed by 8 weeks of treatment and a 24-week follow-up period. At the end of the screening period (at Visit 2), patients meeting the entry criteria for this study will be assigned to treatment with OXERVATE[™] 0.002% (20 mcg/mL) cenegermin-bkbj ophthalmic solution which will be known as Study Product beginning the morning following Visit 2.

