7.1.2. Exploratory Efficacy Endpoints

1. Frequency of preservative free artificial tears use (n° drops/day) during the follow up period.

At selected sites:

The following may be evaluated as part of a post-hoc analysis:

- **2.** Change from baseline structural nerve regeneration (density, length, nerve density, tortuosity) per confocal microscopy.
- **3.** Change from baseline in epithelial thickness per anterior segment OCT.

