2.3 Study Period, Visit, and Day

The overall study consists of initial Screening, a 14-day Washout Period, an 8week Treatment Period, and a 24-week Follow-up Period.

A reference date refers to the date of the first study product administration. All safety and efficacy assessments at all visits will be assigned a day relative to this date. The relative day will be defined as: visit date – reference date + 1 for visits on or after the reference date, and visit date – reference date for visits before the reference date.

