5.3 Exploratory Efficacy Variables

All exploratory efficacy analyses will be performed based on the observed cases in the FAS population.

 Frequency of preservative free artificial tears use (drops/day) during the follow up period

The number of doses of artificial tears used by patients during the follow-up period will be based on the number of used vials recorded in the artificial tears accountability log, and will be summarized as a continuous variable.

• Change from baseline structural nerve regeneration per confocal microscopy

The confocal microscopy images will be examined by an external reading center to be determined, and will be summarized as a continuous variable.

• Change from baseline in epithelial thickness per anterior segment OCT

Exploratory analysis of anterior segment OCT data will be and will be summarized as a continuous variable.

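### SAP 4.3 measures washout artificial-tear use as a first-to-last calendar span, which overstates days of use when there are gap days, ignores frequency and gives non-users no value

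*SAP*

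**What the plan says.** **Washout.** SAP 4.3 states: "Use of artificial tears during the washout period is calculated as days on the use of artificial tears". The formula is "one plus the difference in days between date of last instillation of artificial tears and the date of first instillation", and the result is summarised by descriptive statistics. Table 14.1.7.2 is the only washout tear-use table in the SAP's list. SAP 2.3 describes "a 14-day Washout Period".

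**Permitted use.** The protocol synopsis says that sponsor-supplied tears "will be permitted during the Screening period as needed up to four times a day". For the washout it says that they "will be permitted up to four times a day and will be tracked via daily diary during washout period". Protocol 6.1.1 has the diary dispensed at screening for this purpose, and 6.1.2 has it reviewed at Visit 2. The schedule in protocol section 2 places an evaluation of tear use from the diary at Visits 2 and 7.

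**Follow-up.** The exploratory endpoint in protocol 7.1.2 is "Frequency of preservative free artificial tears use (n° drops/day) during the follow up period". SAP 5.3 keeps that title but says that the number of doses "will be based on the number of used vials recorded in the artificial tears accountability log". The protocol synopsis and section 3.3 track follow-up tear use in the daily diary.

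**The concern.** A first-to-last span is a reasonable measure of duration for a product taken on a fixed schedule. SAP 4.4 uses it that way for study product, and SAP 4.5 then adds a dose count from the study product diary. Artificial tears are the opposite case: use is expected to be intermittent, yet they get the span and no count. Three things are lost:

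- days of use, whenever there is a gap day between the first and last instillation;
- frequency, for every patient;
- any defined value for a patient who needed no tears.

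The table is meant to describe how much lubrication patients needed before treatment. As specified it describes how far apart two dates were. The follow-up endpoint has a related weakness: its unit is drops per day, but its stated source is a count of containers.

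**Working it through.** **Inputs.** The formula is from SAP 4.3. The washout length of 14 days is from SAP 2.3. The range of 0 to 4 instillations a day is from the protocol synopsis. The documents give no figure for tear use, so there is no plan figure to reproduce and no usage rate to insert. Usage patterns and probabilities below are assumptions.

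**Step 1: example patients.** Span = last day − first day + 1. Instillations per day = total ÷ 14.

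| Pattern over 14 days | Span (SAP 4.3) | Days with use | Total | Per day |
|---|---|---|---|---|
| One on day 1 and one on day 14 | 14 − 1 + 1 = 14 | 2 | 2 | 2/14 = 0.14 |
| One every day | 14 | 14 | 14 | 14/14 = 1.0 |
| Four every day | 14 | 14 | 56 | 56/14 = 4.0 |
| Four on each of the last 3 days | 14 − 12 + 1 = 3 | 3 | 12 | 12/14 = 0.86 |
| None | undefined | 0 | 0 | 0 |

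The first three patients all score 14, with totals from 2 to 56. The fourth scores 3, although that patient used six times as many instillations as the first (12 against 2).

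**Step 2: size on average.** Assume that a patient uses tears on each of the 14 days independently with probability q. Then

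- P(span = 1) = 14 q (1 − q)^13;
- P(span = L) = (15 − L) q² (1 − q)^(14 − L) for L = 2 to 14;
- P(no use) = (1 − q)^14;
- mean days of use among users = 14q ÷ [1 − (1 − q)^14];
- mean span among users = Σ L × P(span = L) ÷ [1 − (1 − q)^14].

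For q = 0.2, mean days of use is 2.8 ÷ (1 − 0.044) = 2.93 and mean span is 7.29, so the ratio is 7.29 ÷ 2.93 = 2.49.

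| q (assumed) | Mean span | Mean days with use | Ratio | P(no use) |
|---|---|---|---|---|
| 0.1 | 4.31 | 1.82 | 2.37 | 22.9% |
| 0.2 | 7.29 | 2.93 | 2.49 | 4.4% |
| 0.3 | 9.52 | 4.23 | 2.25 | 0.7% |
| 0.5 | 12.00 | 7.00 | 1.71 | <0.1% |
| 0.8 | 13.50 | 11.20 | 1.21 | <0.1% |
| 1.0 | 14.00 | 14.00 | 1.00 | 0% |

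**Step 3: non-users.** The formula needs two dates that a non-user does not have, and SAP 4.3 does not say whether such a patient counts as zero or as missing. At q = 0.1, mean days of use is 1.82 among users but 14 × 0.1 = 1.4 when non-users count as zero.

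**Step 4: follow-up source.** SAP 5.3 takes doses from used vials. Protocol 6.1.7 lists collection of the diary at Visit 7 but no return of tear containers. Neither document gives a number of drops per container. The stated source therefore does not lead to drops per day without a conversion that the plan does not supply.

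**The case against.** The strongest reply is that SAP 4.3 states its formula openly and the figure is computed as defined. It is a duration, it sits in the section on treatments and medications, and it feeds one background table. It is not an endpoint or a covariate, and SAP 2.10 treats all efficacy analyses as exploratory. This stands, and it limits the weight of the point. A reader might infer that the reported value is a miscalculation. The documents do not support that: the fault is a label and a measure that do not suit as-needed use, and for a patient with no gap days the day count is right.

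Second, 14 days against 2 is a corner case. This also stands. It needs use on exactly the first and last day, and the range in the working is the fairer guide, though that range is itself assumed.

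Third, a reader might infer that the follow-up endpoint lacks a baseline that it needs. The documents do not support that either. Protocol 7.1.2 defines it as use in follow-up only, while neighbouring endpoints say explicitly that they are changes from baseline. A before-and-after contrast would also be confounded. In washout other topical treatment is stopped and tears are capped at four times a day. In follow-up, tear frequency for completely healed patients is at the physician's discretion, and the other patients may receive other topical treatment.

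Fourth, the diary's fields are not shown, so daily counts cannot be taken for granted. Protocol 5.2 requires tear use to be documented in the diary and the eCRF but does not say in what detail. The fix has to be conditional on this. A washout container count may also exist, since bottles are returned at Visit 2, but it would not give days of use.

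**Conclusion.** The point holds as a minor one. The span in SAP 4.3 does not measure as-needed tear use. It overstates days of use for any patient with a gap day, does not distinguish one instillation a day from four, and has no value for a non-user. The average overstatement is about 2.5-fold to 1.2-fold for q between 0.1 and 0.8, and none for daily use. These ratios rest on a 14-day washout and on independent days with one common probability. Real use may cluster, which would change the ratios but not the direction: the span can never be smaller than the number of days with use. Separately, the SAP and the protocol name different sources for follow-up tear use and should be reconciled. The primary endpoint and the sample size are not affected.

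**What to change.** 1. In SAP 4.3 and Table 14.1.7.2, replace the span with the number of washout days on which tears were used at least once, taken from the diary. Provided the diary or eCRF holds daily counts, add mean instillations per day. Count non-users as zero in both, and give the number of diary days as the denominator.
2. In SAP 5.3, reconcile the used-vial source with the protocol's diary tracking, and derive the follow-up endpoint from the diary so that its unit is drops per day. The accountability log can serve as a cross-check.
3. Optionally, show the washout and follow-up values side by side, labelled as descriptive and ideally limited to completely healed patients, with a note that the rules on tears and other treatments differ between the periods.

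If daily counts are recorded, the cost is SAP wording and programming, with no new visit or procedure. If they are not, item 1 reduces to days with use, provided the diary shows these. For item 2, the SAP should then state how containers are converted to drops per day.

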4.4 Extent of Exposure to Study Product

Extent of exposure to study product is calculated as days on therapy, defined as one plus the difference in days between date of last instillation of study medication and the date of first instillation of study medication. For subjects for whom the date of last dose is unknown, extent of exposure will be calculated based on the date of last contact. Extent of exposure to study product will be summarized using descriptive statistics.

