1.3.2.3 Study Drug Administration

The subject will receive a total of 56 OXERVATE[™] 0.002% (20 mcg/mL) cenegermin-bkbj ophthalmic solution vials per treated eye over the 8-week duration of the study product treatment, 1 OXERVATE[™] 0.002% (20 mcg/mL)

cenegermin-bkbj ophthalmic solution vial to be used per day. The patient will pick up Study Product from the Investigator's office and bring back used vials for reconciliation at the subsequent study visit. Patients will be instructed to selfadminister the study product one drop in the affected eye(s) six times a day at 2 hour intervals starting on the day after Visit 2 (Day 0-Baseline and First Study product Pick Up) of the treatment period. On Day 1, the patient will start the first dose. The patient should not start therapy on the same day as Day 0/Visit 2. The Study Product will be dosed one drop (- 0.70 µg/35 µl of cenegermin-bkbj 0.002% solution) 6 times a day at 2-hour intervals in the affected eye(s) for 8 weeks of treatment.

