4.5 Treatment Compliance of Study Product

The overall treatment compliance of study product in the treatment period is calculated as: $100 \times$ The total number of doses / (The total number of days of exposure to study product × 6), where the total number of doses is summed from numbers of daily doses recorded on the Study Product Diary. Overall compliance in the treatment period is categorized as <80%, 80-120%, >120%.

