6.1 Adverse Events

Adverse events data is collected from the time that informed consent was given, for the duration of the trial on the 'Adverse Events' eCRF page. All events in the clinical database regardless of when they occurred will be provided in data listings. Adverse events will be classified according to the MedDRA to the levels of SOC and PT. SOC will be sorted alphabetically and PT within each SOC will be sorted by overall descending order of frequency.

Pre-treatment AEs are defined as AEs that started during the pre-treatment period (date of informed consent up to the time before the first administration of the study product. Pre-treatment AEs, if any, will be listed only.

Treatment-emergent adverse events (TEAEs) are those with onset after the first dose of study product. Only treatment-emergent events will be summarized.

An overall summary will be presented which gives the number and percentage of subjects that experienced any TEAE, experienced any treatment related TEAE, permanently discontinued treatment due to a TEAE, interrupted treatment due to a TEAE, experienced a serious AE (SAE), and AEs leading to death.

The number and percentage of subjects experiencing one or more events will be tabulated by SOC and PT. In addition, similar tables by SOC and PT will be displayed further by maximum severity, and by closest relationship to treatment. For summary, the TEAEs with relationship to treatment reported as "None" or "Unlikely" are considered "Not Related", and "Possible", "Probable", or "Highly Probable" are considered "Related".

Summary tables will be prepared also for the number and percentage of subjects experiencing one or more events classified as: On Treatment Period (AEs started between the day of first administration of the study product and the day of last administration of the study product), and On Follow-up Period (AEs started after the day of last administration of the study product).

In summary tables for ocular adverse events, AEs occurring in both eyes will be summarized once at the greater severity or closer relationship to study drug.

The number of and percentage of subjects experiencing AEs leading to premature discontinuation from the study will be tabulated and listed.

Confidential Final Version 1.0, 2021-05-20

A listing of serious TEAEs will be also provided.

A glossary listing that shows the verbatim terms assigned to each SOC and PT will be provided.

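### SAP 4.4 replaces an unknown last-dose date with the date of last contact and sets no cap at end of treatment, so a 56-day course can be reported as 217 to 231 days of exposure

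*SAP*

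**What the plan says.** SAP 4.4 defines days on therapy as "one plus the difference in days between date of last instillation of study medication and the date of first instillation of study medication". When the end date is not available, it adds: "For subjects for whom the date of last dose is unknown, extent of exposure will be calculated based on the date of last contact". It gives no upper limit and does not say what counts as last contact.

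SAP 4.5 expresses compliance as a percentage. In the numerator, "the total number of doses is summed from numbers of daily doses recorded on the Study Product Diary". The denominator is six times "The total number of days of exposure to study product", a quantity that only SAP 4.4 defines. The result is then banded: "Overall compliance in the treatment period is categorized as <80%, 80-120%, >120" per cent.

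On timing, SAP 1.3.2.3 plans 56 vials per treated eye, one per day, with six drops a day, and states: "On Day 1, the patient will start the first dose". Under SAP 1.2, patients healed at Week 8, and unhealed patients who are not discontinued, continue for a further 24 weeks. Protocol 6.1.7 places the final visit at Day 224 ±7. Protocol 3.3 describes follow-up of healed patients as free of study product and bars retreatment of those not healed. Patients who stop early have the Visit 6 assessments and are then no longer followed (SAP 1.2, Protocol 6.2).

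**The concern.** Last contact is a reasonable stand-in for last dose when contact ends with treatment. In this design it usually does not. A patient who completes follow-up is last seen 224 − 56 = 168 days after the planned last dose, and none of those days involves study product. Whenever the substitution is made for such a patient, off-drug follow-up is counted as drug exposure.

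The same number of days appears to feed compliance. A patient who took every dose could then be tabulated in the lowest compliance band only because an end date was missing. What is at stake is the accuracy of the exposure and compliance tables, which describe how much drug the safety population received.

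**Working it through.** **Inputs**
- First dose: Day 1 (SAP 1.3.2.3).
- Planned course: 56 days, six doses a day (SAP 1.3.2.3).
- Final visit: Day 224 ±7, that is Day 217 to Day 231 (Protocol 6.1.7).
- Exposure = last date − first date + 1 (SAP 4.4).
- Compliance = 100 × doses / (exposure days × 6) (SAP 4.5).
- Planned evaluable sample: 35 (Protocol 9.1).

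**Step 1. Reproduce the plan's own course.** 8 × 7 = 56 vials. Exposure = 56 − 1 + 1 = 56 days. Doses = 56 × 6 = 336. Compliance = 100 × 336 / (56 × 6) = 100%. The formulas behave as intended when the last-dose date is known.

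**Step 2. Apply the fallback to a patient seen at Visit 7, with all 336 doses recorded and the SAP 4.4 days carried into SAP 4.5.**

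| Last contact | Exposure (days) | Multiple of 56 | Compliance |
|---|---|---|---|
| Day 217 | 217 | 3.875 | 336 / (217 × 6) = 25.8% |
| Day 224 | 224 | 4.0 | 336 / (224 × 6) = 25.0% |
| Day 231 | 231 | 4.125 | 336 / (231 × 6) = 24.2% |

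**Step 3. When does a full course fall into the lowest band?** Solve 336 / (days × 6) = 0.80, which gives days = 336 / 4.8 = 70. Any assigned exposure above 70 days puts a fully compliant patient below 80%. Every date in the Visit 7 window does so.

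**Step 4. Illustrative effect on the mean.** Suppose 34 patients have 56 days and one has 224. The mean is (34 × 56 + 224) / 35 = 2128 / 35 = 60.8 days instead of 56, and the reported maximum is 224. The count of one is an assumption; the documents give no rate of unknown last-dose dates.

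**Step 5. Patients who leave during treatment.** Those who discontinue have Visit 6 procedures and then leave the study. Those lost during treatment have their last contact within that period. In both cases last contact is close to the end of dosing, and the rule gives a sensible value.

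**The case against.** The strongest reply is that the rule will seldom be used, and least often for patients who reach Week 32. They have normally passed Visit 6, where the diary and product are collected (Protocol 6.1.6) and vials are inventoried the same day (SAP 1.3.2.4). An unknown last dose is more likely in someone lost during treatment, for whom the rule is harmless. This stands, and it limits the size of the problem. It does not make the rule right for a patient followed to Visit 7.

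The 25% figure also needs a full diary count alongside an unknown last-dose date. A diary with 56 days of entries would usually show the last dosing day, so that combination would be a data discrepancy open to correction. If the final two-week diary is lost, 252 doses are recorded and compliance is 252 / 336 = 75% even against the correct 56 days, so the figure is unreliable under any end date. This too stands. The inflated exposure in SAP 4.4 does not depend on it.

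SAP 4.5 twice describes compliance as being for the treatment period, which can be read as limiting the denominator to eight weeks. That reading is fair, but neither section states the limit, and the denominator is exposure days as defined in SAP 4.4.

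A reader might also infer that follow-up adverse events and medications would be moved into the treatment period. The documents do not support this. The SAP 4.4 sentence is limited to extent of exposure. SAP 6.1 assigns events by the actual last administration, "On Follow-up Period (AEs started after the day of last administration of the study product", without referring to SAP 4.4, and SAP 4.2 does the same for medications. SAP 2.11 imputes start and stop dates of events and medications, never the last dose. The splits therefore have no rule for an unknown last dose, which is a gap and not a stated misclassification.

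**Conclusion.** The rule is wrong as written, with low impact. For a patient followed to Visit 7 whose last-dose date is unknown, SAP 4.4 yields 217 to 231 days of exposure for a planned 56-day course. Compliance of about 24 to 26% follows only if SAP 4.5 uses those days and all 336 doses are in the diary. The shift in mean exposure from 56 to 60.8 days rests on an assumed single case in 35.

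The effect is on Tables 14.1.7.1 and 14.1.7.3. It would be wrong to infer that efficacy is touched: the Full Treated Set is defined by treatment through Visit 6 and not by a compliance threshold, no subgroup analyses are planned, and the study is declared exploratory. Nor does it alter the protocol's discontinuation criterion for poor compliance, which uses diary doses between treatment visits (Protocol 6.2) and not the SAP 4.5 result.

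**What to change.** In SAP 4.4, replace the last-contact sentence with an ordered rule for an unknown last-dose date:
1. Use the last dosing date recorded in the diary.
2. If that is missing, use the date of Visit 6 or of the discontinuation visit.
3. If there was no such visit, use the date of last contact, capped at the planned end of the treatment period.

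State in SAP 4.5 that the denominator uses the same exposure days. For consistency, state in SAP 4.2 and 6.1 that the same end date applies to the period splits.

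The wording should also say which step applies when only the final two-week diary is missing, because the choice changes the result. Ending at the last recorded entry (Day 42) gives 42 days and 252 / (42 × 6) = 100%. Ending at Visit 6 on Day 56 gives 56 days and 75%.

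The cost is a few lines of SAP text and a small programming change. Diary and visit dates are already collected, so no new data are needed. Only a derived date changes.
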